9.4.2 ANALYSIS OF THE PRIMARY ENDPOINT(S)

- a) Administrative Claims
 - a. Outcome variables of interest
 - i. Opioid misuse- “Overlapping Rx” OR “Multiple Rx on same day, different provider”
 - ii. Chronic opioid use- more than 60 days supply in a 90 day window
 - iii. Opioid use disorder- ICD-10 T40* (Poisoning by, adverse effect of and underdosing of narcotics and psychodysleptics) &/Or ICD-10 F11* (opioid related disorders) &/or prescribed MAT (Drug name contained “methadone” or “buprenorphine”; picks up buprenorphine, suboxone, zubsolv, naltrexone, methadone, narcan, and vivitrol)
 - b. Compute statistics for baseline period (06/01/2019-05/31/2022) and follow-up (06/01/2022-05/31-2023)

- i. Categorical data will be presented as N (%), continuous data as median (25th, 75th %tile)
- c. Run comparisons between baseline and follow-up time points
 - i. Comparisons involving two categorical variables will be made using Fisher's exact test
 - ii. Comparisons involving a continuous variable and a categorical variable will be made using Wilcoxon Rank Sum test or Kruskal Wallis test

b) Worker Survey

- a. Outcome variable of interest
 - i. Opioid misuse- Participant responded yes to one of the following two questions:
 - 1. Did you use the pain medication more than prescribed, or for a longer period than prescribed? [pnmed_longer]x
 - 2. Have you used prescription pain medications that were prescribed to someone else? [pnmed_othersrx]x
 - b. Compute the change at 6 months post-intervention (change of opioid misusep) of group-level data collected from groups of health

All endpoints are independent outcomes.

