1 PROTOCOL SUMMARY

Title:	Improving Health and Employment Outcomes Through Workplace Opioid Policies
Grant Number:	1R34DA050044-01
Study Description:	We will implement the intervention in three local union health funds, evaluate the implementation using the RE-AIM framework, and collect the data needed to measure effectiveness of the workplace opioid guidelines. We will measure a) the health fund's adoption of policies and programs; b) opioid prescriptions, chronic opioid use, and OUD in health claims and pharmacy data; c) changes in knowledge, attitudes, and beliefs of employers, health fund administrators, and employees; and d) employee participation in employee assistance programs and healthcare recovery services.
Objectives*:	The overall aim is to evaluate the feasibility of implementing workplace opioid guidelines in the construction trades; define and collect measures of implementation and effectiveness. The primary objective is to evaluate a change in opioid misuse and opioid use disorder from medical and pharmacy claims, and worker surveys following a change in policies and programs within health funds. The secondary objective is to evaluate a change in lost time and willingness to seek help among workers who are struggling with opioid misuse or substance use problems on worker surveys.
Endpoints*:	The primary endpoints are a) the change in the proportion of workers with opioid misuse, opioid use disorder and opioid overdose: administrative data and b) in the proportion of workers with opioid misuse: worker surveys from baseline to 6-months. The secondary endpoints are a) the change in the proportion of workers with lost time: worker surveys and b) the proportion of workers who are willing to seek help: worker surveys from baseline to 6-months.
Study Population:	Participants will be members of three participating union health funds. We anticipate these unions will have 33300 members enrolled between 2019-2023, which is the period of data used for the trial. All union members of the participating health funds will be enrolled in the study. We expect the demographics of the participants will reflect the demographics of the membership, which is approximately 8% female, and 90% Caucasian. All participants will be located within the geographical region of the union membership.
Phase* or Stage:	This is a feasibility trial.

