1.2 SCHEDULE OF ACTIVITIES

	Baseline	Visit 1 Day 1	Visit 2 Day 30±7	Visit 3 Day 60±7	Visit 4 Day 90±7	Visit 5 Day 120±7	Visit 6 Day 150±7	Visit 7 Day 180±30	Visit 8 Day 360±30
Enroll Union Health Funds	X								
Sign Data Transfer and Use Agreement (DUA)	X								
Interview Health Administrator	X								
Collect medical and pharmacy claims	X								X
Collect worker surveys	X							X	
Complete process assessment		X	X	X	X	X	X	X	X
Outcome Evaluation									
Opioid misuse and opioid use disorder from administrative claims	X								X
Opioid misuse from worker survey	X							X	
Self-reported lost work time from worker survey	X							X	
Self-reported willingness to seek help from worker survey	X							X	

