9 STATISTICAL CONSIDERATIONS

9.1 STATISTICAL HYPOTHESES

This is a feasibility trial to evaluate the ability to recruit and enroll health funds, collect endpoint data for primary and secondary outcome measures, and to collect process measures related to implementation of the intervention with three health funds. There is no formal hypothesis testing in this trial although we will calculate descriptive statistics at baseline and follow-up (6-months) to show change over time. The data will be used to compute statistical power for a future R01 if the current study is successful.

- Primary Endpoint(s):
 - a) We will calculate the Proportion of workers with opioid misuse, opioid use disorder and opioid overdose using administrative data. We will assess change of opioid misuse and opioid use disorder at 6 months following delivery of the intervention
 - b) We will calculate the proportion of workers with opioid misuse from worker surveys. We will assess change in opioid misuse at 6 months following delivery of the intervention.

- Secondary Endpoint(s):
 - a) We will calculate the proportion of workers with lost time using worker surveys. We will assess change in reported lost time at 6 months following delivery of the intervention.
 - b) We will calculate the proportion of workers reporting willingness to seek help for opioid abuse using worker surveys. We will assess change in reported willingness to seek help at 6 months following delivery of the intervention.

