<https://kentuckycomeback.com/wp-content/uploads/2020/08/Kentucky-Comeback-Employer-Inventory-Form-1.pdf>
- **Kentucky Comeback: Policy and Procedures Samples:** Samples documents for different policies and procedures when employers are developing written policy for their workplace substance use and opioid programs
<https://kentuckycomeback.com/policies-procedures/>
- **Minnesota Department of Health- Opioid Epidemic Response: Employer Toolkit** offers pre made social media posts and communication tools
<https://www.health.state.mn.us/communities/opioids/communities/employertoolkit.html#Example1>

Employee Engagement Surveys

- ***The Boston Medical Center: Employer Survey on Employee Support for Substance Use and Mental Health Disorders***
https://www.bmc.org/sites/default/files/addiction/1-employer-survey_v2.pdf
- ***The Boston Medical Center: Focus Group Discussion Questions:*** Questions for Focus Group on mental health and substance use
<https://www.bmc.org/sites/default/files/addiction/1-focus-group-discussion-questions.pdf>
- ***NSC: Sample Employee Engagement Survey:*** A survey to understand employees knowledge and attitudes on Opioids in the workplace.
<https://www.nsc.org/getmedia/c2d74fc8-1027-4c29-afab-5cedfc07c3a1/sample-employee-engagement-survey.pdf.aspx>

Naloxone Training

- ***NSC Opioids at Work: Naloxone in the Workplace:*** Guides employers on how to develop a Naloxone workplace program <https://www.nsc.org/getmedia/2b1616a1-c8a6-4c8c-b56b-1aa32f395bd5/naloxone-in-the-workplace.pdf.aspx>
- ***Reverse Overdose Oregon: Naloxone Training:*** Documents and training videos that train individuals on how to use Narcan "Naloxone" and what to do in the situation of an overdose <https://www.reverseoverdose.org/training-video>

NOTE: State Specific Employer Resources may be found on page 41.

15 PROGRAM CONTENT GUIDE:

Essential Elements for a Workplace Opioid Prevention Program

[figure not shown]

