15.1.1 STRATEGIES: EMPLOYEE EDUCATION

1. Training may be delivered by human resources, occupational health, or a representative from the EAP/MAP. Trainings may be offered using online or virtual options.
2. The large number of topics that should be included in a comprehensive opioid education program may not be adequately covered or well-understood if delivered in a single session. Provide single topic or short training sessions and repeat trainings on various topics regularly throughout the year.
3. General opioid education can be part of the new hire onboarding process and should be regularly included in team/staff meetings, and other trainings or briefings such as toolbox talks.
4. Educational materials and promotional information may be posted throughout the workplace and through other communication channels (i.e. newsletters, email, texts).

Resources:

[CPWR Opioid Awareness Training Program for Employees](#)

[Nevada Recovery Friendly Workplace Toolkit- "Lunch and Learn"](#)

[Shatter Proof Educational Video Modules on Addiction](#)

[A Dose of Reality for Employees Video Training Module](#)

Other special considerations for employee education:

- Provide employees a means to dispose of excess opioids safely to reduce potential for opioid misuse (Resource: [FDA Drug Disposal Locations Website](#), contact your local hospital or pharmacy, [Stericycle drug disposal envelopes](#)).
- Order “[Warn Me Labels](#)” from National Safety Council to place on insurance cards

- Implement a Workplace Naloxone Program (Resource: [*NIOSH Using Naloxone to Reverse Opioid Overdose Factsheet, Reverse Overdose Oregon Naloxone Training Program*](#))
- Use destigmatized language to grow a caring culture toward substance use disorders (Resource: [*NIDA Words Matter- Terms to Use and Avoid When Talking About Addiction*](#))
- Special topics such as Naloxone training may be offered by a qualified person from a local hospital, first responder, police department, or community organization for recovery or drug use (Resource: [*NIOSH Using Naloxone to Reverse Opioid Overdose*](#))

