 - 1. Serial prescriptions (most common scenario)
 - a. Start with all opioid first fills (including unlinked and linked with medical claims, using the process above)

- b. Arrange all fills by UID and fill date
 - c. Assign fills to claims that 1) occur after a claim with a linked opioid fill, and 2) opioid fill date is no more than 30 days after previous fill runout date (fill date + days supply)
2. Refills specified in the pharmacy data
 - a. Join opioid refills (from 1b above) with the first fills using prescription identifier ("RXNUM").
 - b. Assign claim information from first fills to linked refills

Variable definitions

- e. Opioid-related variables. These variables were generated using information from the medical claims and pharmacy fill data from the health fund and the CDC opioid file "CDC opioid NDC_oral MME conversion_update_2020.xlsx". The CDC file was merged with health fund pharmacy fill data on NDC
 - i. Medication assisted treatment (MAT): Drug name contained "methadone" or "buprenorphine" in either file or drug description was "ANTIDOTES AND SPECIFIC ANTAGONISTS" in the pharmacy fill file
 1. This strategy picks up buprenorphine, suboxone, zubsolv, naltrexone, methadone, narcan, and vivitrol
 - ii. Opioid: pharmacy class was "opioid" in the CDC file, and the drug was not already identified as MAT (see above)
 - iii. OUD: ever ICD-10 code "T40x" or "F11x" on a medical claim or identified as MAT (see above)
 - iv. Days supply > 7 days: based on "days supply" as provided in fill data
 - v. MME/day: Instructions for calculation are in CDC file. Formula is "strength per unit" * "average quantity per day" * "MME conversion factor"
 - vi. Overlapping Rx: Date opioid fill is within previous days supply (current fill date < previous fill date + days supply)
 1. When the previous prescription is a "short course" (the prescription window is encompassed by prescription before it), the prescription before the short course is used in evaluation
 - vii. Chronic use (>60 days supply in a 90 day window)
 1. For each worker time is divided into 90 day "cycles", starting with the date of the first opioid fill
 2. Days supply is totaled within the 90 day cycle
 3. If the individual had opioid fills later than 90 days after the first fill, a new cycle is started and the process starts over
 4. When workers have multiple opioids filled on the same day, use the longest days supply in calculations

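### The claims OUD outcome counts a naloxone (Narcan) fill alone as OUD, and opioid overdose, a named primary claims endpoint, has no variable or result of its own

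*Combined protocol and SAP*

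**What the plan says.** **OUD in claims.** Section 9.4.2 lists three claims outcomes: misuse, chronic opioid use and OUD. Section 9.4.1 calls all three primary. OUD is set by T40*, by F11* or by a MAT prescription, and the MAT search "picks up buprenorphine, suboxone, zubsolv, naltrexone, methadone, narcan, and vivitrol". The data management appendix says the same ("This strategy picks up buprenorphine, suboxone, zubsolv, naltrexone, methadone, narcan, and vivitrol") and sets OUD if either code ever appears on a medical claim or the member is identified as MAT. No diagnosis is needed when there is a MAT fill.

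**Naloxone.** The guidelines in the same document equate Narcan with naloxone: section 14.6 points to materials that "train individuals on how to use Narcan 'Naloxone' and what to do in the situation of an overdose". The Critical Incident Response Plan text describes naloxone as reversing an overdose. The text on treatment and recovery from OUD names three recovery medications (buprenorphine, naltrexone, methadone), and naloxone is not one of them.

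**Overdose.** It is named as a primary claims endpoint in the Protocol Summary (Endpoints), in the text and the table of section 3, and in the calculation sentence of 9.1. Other statements leave it out:
- the Protocol Summary objective: "evaluate a change in opioid misuse and opioid use disorder from medical and pharmacy claims"
- the Protocol Summary study description: "opioid prescriptions, chronic opioid use, and OUD in health claims and pharmacy data", repeated in section 2.1
- the Schedule of Activities: "Opioid misuse and opioid use disorder from administrative claims"
- the second sentence on claims in 9.1: "We will assess change of opioid misuse and opioid use disorder at 6 months following delivery of the intervention"

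**The concern.** A naloxone fill shows that someone wanted the means to reverse an overdose. It does not show that the member has OUD. Counting it as OUD puts a preventive supply into a disease proportion.

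Separately, a reader of section 3 or 9.1 expects three claims results, one of them overdose. An analyst who follows 9.4.2 and the appendix will not produce that one.

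The OUD flag also combines diagnoses with treatment fills. The guidelines promote coverage of OUD medication (needs assessment in 14.1, strategies in 15.1.3, and the treatment and recovery text), while 9.4.1 looks for a reduction as the sign of benefit. More members treated could raise the flag, so its components are needed to read any change. At stake are the meaning of a primary proportion and the rates carried into the power calculation for the future trial.

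**Working it through.** The point concerns definitions, so the check is mainly a comparison of texts. The plan gives no figure to reproduce.

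**1. Trace of the rule.** Narcan fill only → MAT = yes → OUD = yes, under both 9.4.2 and the appendix. Of the 7 products listed, the documents identify 1 (Narcan) as naloxone.

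**2. The two wordings of the MAT rule.** Section 9.4.2 prints only a name match on methadone or buprenorphine. As text strings, narcan, naltrexone and vivitrol contain neither word; nor do suboxone and zubsolv, unless the recorded drug name also carries one of the two terms. The appendix searches two files and adds a drug-description class for antidotes and antagonists, which can bring in the remaining products. Both texts state the same resulting list, so 9.4.2 is an incomplete abbreviation of the appendix rule.

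**3. Overdose, by count.**
- Statements naming it as a primary claims endpoint: 4 (Protocol Summary endpoints; section 3 text; section 3 table; 9.1 calculation sentence).
- Statements of claims outcomes without it: at least 5 (Protocol Summary objective; Protocol Summary study description; Schedule of Activities; section 2.1; 9.1 change sentence).
- Claims outcomes in 9.4.2 that are overdose: 0 of 3.
- Opioid-related variables in the appendix that are overdose: 0 of 10.
- Rows for overdose in the appendix's list of sample descriptions: 0.

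**4. Where overdose codes go.** T40* is a component of OUD. By the label printed in 9.4.2 it covers adverse effects, underdosing and psychodysleptics as well as poisoning. Overdose codes are therefore collected, but T40* is not itself an overdose definition, and no planned output isolates overdose.

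**5. What the by-source count gives.** The appendix reports the number with OUD by diagnosis, by MAT fill or by both. This separates diagnosis from MAT fills. It does not split naloxone from OUD medication or T40 from F11, and it is not stated by period. The appendix inclusion rule gives the study period as 1 June 2019 to 31 May 2022, which is the baseline period in 9.4.2.

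**6. Size.** The documents give no OUD rate and no naloxone fill rate. On purely assumed rates, relative change in the flag = (follow-up OUD + follow-up naloxone-only) / (baseline OUD + baseline naloxone-only) − 1. Without naloxone-only members, both assumed falls below are −20%.

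| Assumed OUD without naloxone-only | Naloxone-only 0.1% → 0.1% | 0.1% → 0.3% | 0.1% → 0.5% |
|---|---|---|---|
| 1.0% → 0.8% | 0.9/1.1 − 1 = −18% | 1.1/1.1 − 1 = 0% | 1.3/1.1 − 1 = +18% |
| 2.0% → 1.6% | 1.7/2.1 − 1 = −19% | 1.9/2.1 − 1 = −10% | 2.1/2.1 − 1 = 0% |

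The result depends entirely on the assumed growth in naloxone-only members. With no growth the distortion is one or two percentage points of relative change. The table shows the mechanism and is not an estimate for these funds.

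**The case against.** **Narcan under MAT has some support in the text.** The Terms List defines MAT as covering the prevention of overdose as well as treatment, and Narcan is named in both the plan and the appendix, so its listing looks deliberate. This explains the grouping. It does not make a naloxone fill evidence that the member has OUD, which is what the flag asserts.

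**A reader might infer that the intervention will push the OUD proportion up through naloxone and hide a benefit.** The documents do not support this. They give no fill rates, and they promote naloxone mainly as a workplace measure ("Implement a Workplace Naloxone Program" in 15.1.1, and the Critical Incident Response Plan), not as fills paid by the members' plan.

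**A reader might infer that the two MAT wordings give different OUD counts.** Both state that Narcan is picked up, and section 8.1 refers to the appendix for data management. The mismatch is editorial.

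**A reader might infer that disease and treatment cannot be told apart at all, or that overdose is not captured.** The by-source count partly answers the first. On the second, overdose codes are captured within T40* but not reported separately.

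**A reader might infer that chronic use was quietly substituted for overdose.** Chronic use is a declared claims measure in the Protocol Summary and section 2.1. The texts show lists that disagree and say nothing of intent.

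**This is a feasibility study.** Section 9.1 states that there is no formal hypothesis testing, and section 9.2 that there was no power calculation. That limits the consequence and stands. It does not supply a missing definition for a named primary endpoint.

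**Conclusion.** The point holds on two counts that can be read directly from the text: a naloxone fill alone sets the primary claims OUD flag, and a named primary claims endpoint, overdose, has no variable and no result. The endpoint lists also disagree with one another. The request for OUD components by period is a smaller reporting point, and the MAT wording is editorial.

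No size or direction of bias is shown. The consequence is for interpreting the OUD proportion, for the absent overdose result, and for the rates passed to the future trial. The conclusion assumes only that 9.4.2 and the appendix are followed as written. It should be fixed before the claims analysis is run or reported.

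**What to change.** - **Naloxone.** Remove naloxone-only fills from the OUD flag in 9.4.2 and in the appendix.
- **Overdose.** Define claims-recorded opioid overdose from the opioid poisoning codes within T40, excluding adverse-effect, underdosing and non-opioid codes. Report it separately by period, and state that overdoses without a claim are missed.
- **T40* in OUD.** State explicitly whether T40* stays in the flag. If it is removed, say that members flagged only by T40* leave the OUD outcome, and report OUD both ways.
- **Components.** Beside the OUD result, report F11*, T40*, OUD-medication fills and naloxone fills for each period, with the same adjustment for period length as in 9.4.1.
- **Consistency.** Reconcile the claims endpoint lists in the Protocol Summary, the Schedule of Activities and sections 2.1, 3, 9.1, 9.4.1 and 9.4.2, including the status of chronic opioid use. Make the MAT rule in 9.4.2 match the appendix.

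The cost is recoding plus edits to the text. Diagnosis codes, drug names and drug identifiers are already in the requested variable list. That list has no death field, so an overdose that generates no claim stays outside the measure. There will be somewhat fewer OUD cases, and no claims definition fully separates disease from care-seeking.
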